### 6.5 Criteria for Removal from Protocol Therapy and Off Study Criteria

# **6.5.1** Criteria for Removal from Protocol Therapy

In the absence of treatment delays due to adverse event(s), treatment may continue for to a maximum of 12 cycles (9 months of combination therapy) [except in cohort B4, resectable, pulmonary only relapsed osteosarcoma, who may continue combination therapy for a total of 5 cycles after pulmonary resection] or until one of the following criteria applies:

Disease progression

- Intercurrent illness that prevents further administration of treatment.
- Unacceptable adverse event(s), including, but not limited to, any one of the following:
  - o Patients who have Grade 4 infusions reactions occurring with the first dose of Hu5F9-G4 (magrolimab) or dinutuximab will be permanently discontinued from treatment.
  - Patients who receive Hu5F9-G4 (magrolimab) premedication with corticosteroids and still have a Grade 3 or 4 infusion reaction on subsequent doses will generally be permanently discontinued from treatment, unless continued therapy is approved by the Study PI, Site PI and Sponsor.
  - O Patients who receive dinutuximab and experience any of the AEs listed in Table 8: Adverse Reactions Requiring Permanent Discontinuation of Dinutuximab

or recur after appropriate management as outlined in Section 7.3.2.

- Patient who develops a DLT during the "single agent Safety Lead-In" will be removed from additional therapy on this study.
- General or specific changes in the patient's condition render the patient unacceptable for further treatment in the judgment of the investigator.
- Clinical progression of disease
- Patient non-compliance
- Pregnancy
  - All women of childbearing potential should be instructed to contact the investigator immediately if they suspect they might be pregnant (e.g., missed or late menstrual period) at any time during study participation.
  - The investigator must immediately notify CTEP in the event of a confirmed pregnancy in a patient participating in the study.
- Termination of the study by sponsor
- The drug manufacturer(s) can no longer provide the study agents.

#### **6.5.2** Off Study Criteria

- a) Thirty days after the last dose of the investigational agent for patients who develop disease progression during combination therapy.
- b) The fifth anniversary of the date the patient was enrolled on this study, or until disease progression, for patients who complete the maximum number of cycles or who met off protocol therapy criteria in Section 6.5.1 other than disease progression.
- c) Withdrawal of consent for any required observations or data submission.
- d) The patient does not receive protocol treatment after study enrollment.
- e) Patient enrollment onto another COG study with therapeutic (anti-cancer) intent.
- f) Lost to follow-up.
- g) Death

The reason(s) for removal from protocol therapy, the reason(s) for the patient being off study, and the corresponding dates must be documented in the Case Report Form (CRF).

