## 6.6 **Duration of Follow-Up**

Patients who complete the maximum number of cycles or who met off-therapy criteria other than disease progression will be asked to participate in study follow-up and be evaluated at month 2 ( $\pm$  1 week), month 4 ( $\pm$  2 weeks), month 6 ( $\pm$  4 weeks), month 9 ( $\pm$  4 weeks), and month 12 ( $\pm$  2 months) and then yearly until year 5, or until disease progression.

Follow-up visits will be completed in-person unless the patient does not agree to continue in-person visits. In this case, telephone contact may be arranged to ensure the collection of as many safety and efficacy parameters as possible. The approach taken should be recorded in the CRF. A patient that agrees to modified follow-up is not considered to have withdrawn consent or to have withdrawn from the study.

Patients who develop disease progression during combination therapy will be followed for a minimum of 30 days after the last dose of study drug or study procedure, or until death, whichever occurs first. Patients removed from study for unacceptable adverse event(s) will be followed until resolution or stabilization of the adverse event and disease progression, whichever occurs later.

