Magrolimab activates macrophages as does dinutuximab. Given that dinutuximab causes pain due to GD2 expression on normal nerve cells, there is a theoretical potential for worsening of this pain or other neurologic toxicity such as motor dysfunction or permanent damage to peripheral nerve cells.

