-  Karnofsky score of ≥50% is required for patients >16 years, and Lansky score of ≥50% is required for patients ≤16 years. Patients unable to walk due to paralysis, but who are using a wheelchair, will be considered ambulatory for the purpose of assessing the performance score. See APPENDIX A.
- Baseline disease evaluation will occur within 28 days of treatment initiation. During the treatment period Cycles 1 through 4, patients should be re-evaluated for response at the end of Cycles 2 and 4. After Cycle 4, disease evaluation will occur every 12 weeks (after every 4 cycles). Disease evaluations should occur within 7 days prior to dosing of the subsequent cycle. If treatment is delayed, disease evaluations will follow the originally scheduled calendar dates and should not be adjusted for the dose delay. The same method of assessment and technique should be used throughout the study. See Section 12 for disease parameters, methods of assessment, and response criteria. For patients with neuroblastoma/ganglioneuroblastoma, bilateral bone marrow aspirates and trephine biopsies are required at all disease assessment time points (see Section 12.2) and Follow-up Visits for disease evaluation.
- Confirmatory scans should also be performed according to Section 12 in patients with measurable disease. The same method of assessment and technique should be used throughout the study.
- All AEs occurring within 30 days after the last dose of the study drug must be reported in a routine manner using Rave. Additionally, all AEs that occur within 30 days after the last dose of the study drug, regardless of causality, meeting the expedited reporting criteria outlined in Section 10.3 must also be reported expeditiously via CTEP-AERS.

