  - Patients removed from protocol therapy for unacceptable AE(s) will be followed until resolution or stabilization of the AE. In addition, these patients will complete the EOT, Safety, and Follow-up Visits according to protocol.
- All blood draws for correlative exploratory biology studies will be performed according to the schedule outlined in Table 3, Specimen Collection Schedule; and Section 5. All blood draws for correlative exploratory biology studies must be performed prior to dosing. If treatment is delayed, blood draws for correlative exploratory biology studies will follow the originally scheduled calendar dates and should not be adjusted for the dose delay.
- Archival slides will be requested from all patients. If available, clinical biopsies or surgical samples obtained during treatment or at disease progression will be requested.
-  After Cycle 2, Hu5F9-G4 (magrolimab) will be administered ONLY on Day 1 of week 1 and 3 only (week 2 will be a week of rest).
- Bone marrow aspirations will be conducted in all patients with neuroblastoma/ganglioneuroblastoma (as per INRC). Week 1, Day 1 collection is mandatory, *except* if viably frozen bone marrow aspirate collected within 4 weeks (28 days) of the Priming dose (Week 1, Day 1) is available and can be provided to the EET Biobank. Bone marrow aspirates are required at all disease assessment timepoints (end of Cycle 2, 4, 8 and 12). Bone marrow aspirate at End of Therapy is optional.
- Within 24 hours prior to the Priming dose (Week 1) of Hu5F9-G4, hemoglobin must be ≥ 9.5 g/dL. Within 24 hours prior to the first full dose (Week 2) of Hu5F9-G4, hemoglobin must be ≥ 9.0 g/dL (see Section 6.2.1.3). Hemoglobin must be checked 3 to 6 hours after the initiation of the first and second doses of Hu5F9-G4 (magrolimab).

THIS PROTOCOL IS FOR RESEARCH PURPOSES ONLY, SEE PAGE 1 FOR USAGE POLICY

Baseline/screening evaluations are to be conducted within 4 weeks (28 days) prior to start of protocol therapy. Scans must be done < 4 weeks (28 days) prior to the start of protocol therapy. In the event that the patient's condition is deteriorating, laboratory evaluations should be repeated within 48 hours prior to initiation of the next cycle of therapy.

Treatment Cycles/Visits	Screening	Treatment								Follow Up		
		Priming Cycle 1				Cycle 2 and subsequent cycles			End of	G 6 /	E II II 17	

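### The off-study rules in Section 6.5.2 conflict with the adverse-event follow-up in Section 6.6 and the study calendar when a patient progresses with toxicity unresolved

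*Combined protocol and SAP*

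**What the plan says.** The combined protocol and SAP sets the end of observation in several places.

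- **Section 6.5.2, item (a)**, patients who progress on combination therapy: "Thirty days after the last dose of the investigational agent for patients who develop disease progression during combination therapy".
- **Section 6.5.2, item (b)**, patients who stop therapy for any other reason: the fifth anniversary of enrollment, "or until disease progression, for patients who complete the maximum number of cycles or who met off protocol therapy criteria in Section 6.5.1", progression itself excepted. Unacceptable toxicity is one of the 6.5.1 criteria, so toxicity removals fall under (b).
- **Section 6.5.2, item (e)**: enrollment on another COG anticancer study ends participation, with no minimum period. None of these three items mentions an adverse event that is still open.
- **Section 6.6**: on-treatment progressors "will be followed for a minimum of 30 days after the last dose of study drug or study procedure, or until death, whichever occurs first". By contrast, the group taken off because of toxicity "will be followed until resolution or stabilization of the adverse event and disease progression, whichever occurs later".
- **Section 11, footnotes for both arms**: "Patients removed from protocol therapy for unacceptable AE(s) will be followed until resolution or stabilization of the AE" (footnote 17), and "All AEs occurring within 30 days after the last dose of the study drug must be reported in a routine manner using Rave" (footnote 12). The Safety Visit is scheduled 30 days after the last dose, plus or minus 7 days.
- **After day 30**: the first footnote to the expedited-reporting table in Section 10.3.3 requires related serious events to be reported, and Section 13.2.2 provides a Late Adverse Event form.

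**The concern.** Safety and tolerability of the combination is the first primary objective (Section 1.1.1). The end of Section 10.1.1.2 names, as a theoretical risk of giving the two antibodies together, worse pain or other "neurologic toxicity such as motor dysfunction or permanent damage to peripheral nerve cells". The importance of such an event depends largely on whether it resolves. The protocol uses persistence in this way itself: Table 8 makes Grade 3 sensory neuropathy a reason to stop dinutuximab when it interferes with daily activities beyond 2 weeks, and a CAEPR footnote describes chronic urinary retention needing catheterization days to weeks after dosing.

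If the off-study date arrives before the event has settled, the record holds onset and grade but not outcome. That would happen only in patients who progress or move to another trial, so the missing outcomes would not be a random subset.

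**Working it through.** The documents state no figure to reproduce. The check sets the passages side by side and does day arithmetic from the last dose.

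**1. Toxicity removal, then progression before the event resolves.**

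| Source | End of follow-up |
|---|---|
| 6.5.2(b) | progression (or year 5) |
| 6.6 | the later of resolution or stabilization and progression |
| Section 11, footnote 17 | resolution or stabilization of the event |

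If progression falls at time P and resolution at time R with P < R, item (b) gives P, while 6.6 and the footnote give R. The rules cannot all be met. If R ≤ P, (b) and 6.6 agree. The wording also differs: 6.6 speaks of removal from study, the footnote of removal from protocol therapy.

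**2. The 30-day window under items (b) and (e).** If a patient goes off study d days after the last dose, with d < 30, the window still to run is 30 − d days:

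- d = 7: 23 days
- d = 14: 16 days
- d = 21: 9 days

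Neither item carries a floor at day 30. Under (b) this needs progression to be found early. Section 12 schedules the first disease evaluation after therapy at month 2, so early progression would come to light clinically or on a scan already due.

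**3. Item (a).** Off study at day 30 against a 30-day window: 30 − 30 = 0 days lost. Counted from the last dose, it also meets the 6.6 minimum. It differs from 6.6 in making that minimum an end date. (Section 6.6 also lets the clock start at the last study procedure, which (a) does not mention.)

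**4. Safety Visit.** The window is 30 − 7 = day 23 to 30 + 7 = day 37. A visit on days 31 to 37 is within window, yet up to 7 days after the off-study date under (a).

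**5. Follow-up to resolution for on-treatment progressors.** Section 6.6 gives this group no such clause, and (a) adds none. This is a gap, not a contradiction.

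**6. How many patients.** The relevant count is patients who progress and also have an unresolved related event when they go off study. The documents give no rate for the second condition. The only related figure is the historical event-free survival in Section 9.5.3, 12% at 4 months (95% CI 6% to 19%). If cohort B3 behaved the same way, 20 × (1 − 0.12) = 17.6 of 20 patients would have an event by 4 months (16.2 to 18.8 across the interval). That describes how many B3 patients might progress, and only if nearly all events are progressions on treatment. The number with toxicity outstanding lies somewhere between none and that total.

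**The case against.** **Item (a) breaks no stated rule.** A reader might infer that it contradicts the 30-day window. It does not: it ends exactly at the window and meets the 6.6 minimum. This stands, and the contradictions are in (b) and, for the window, (e).

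**Nerve injury is largely covered.** Section 7.3.2.10 and Table 8 stop treatment for the serious neuropathies, which makes these patients toxicity removals, followed to resolution under 6.6 and footnote 17. Section 6.6 can even be read as continuing after off-study status. A reader might infer that the rules hide how often nerve injury persists; the documents do not support that. Still, this is the group for whom (b) gives the opposite instruction once they progress, and nothing says that 6.6 prevails.

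**Not every progressor is cut off early.** A reader might infer that outcomes stop by day 30 in all patients who progress. Under (b), follow-up runs to progression, which may come months or years later. This stands.

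**Reporting duties survive going off study.** Footnote 12 counts from the last dose and has no off-study exception, adverse-event evaluation is continuous, and related serious events after day 30 remain reportable. This limits the loss. However, the late rule covers serious events that occur after day 30, not the outcome of an earlier or non-serious one, and neither it nor the Late Adverse Event form schedules a contact.

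**No analysis of duration is planned.** Section 9.2.1 summarizes events by type and severity, so no stated analysis is biased. That is right; what is at risk is the collected record.

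**The size cannot be read from event-free survival or half-life.** A reader might take 17.6 of 20, or the half-life of about 2 weeks in Section 2.1.6, as measuring the harm. The first does not count unresolved toxicity and concerns one cohort. The second is magrolimab's, while the nerve and urinary effects cited are dinutuximab's.

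**Conclusion.** The concern holds as a conflict between passages, with a gap beside it. Item (b) contradicts 6.6 and footnote 17 for a toxicity removal who progresses before the event resolves. Items (b) and (e) can end participation inside the 30-day window. Item (a) turns a minimum into an end date that the Safety Visit can overrun by up to 7 days.

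The consequence is that the outcome of unresolved related toxicity can go uncollected in patients who progress. This assumes that sites apply 6.5.2 as written. How many patients this affects cannot be derived from the documents. It should be corrected because safety is primary and the correction is cheap. The dose decision is not affected, since each DLT window is 21 days on treatment, nor is event-free survival, which already ends at progression.

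**What to change.** Reconcile Section 6.5.2 items (a), (b) and (e), Section 6.6, and the Section 11 calendars with footnotes 12 and 17, so that:

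- the off-study date does not precede the end of the 30-day adverse-event window or the Safety Visit;
- adverse-event follow-up of patients removed for toxicity has the same end point everywhere, with one term for removal from therapy and another for going off study;
- the protocol states whether that follow-up also applies to on-treatment progressors with an unresolved related event.

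The choice of follow-up rule is the sponsor's; the passages need only agree. The means are already there: Section 6.6 allows telephone contact, and the Late Adverse Event form can hold the result.

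The cost is wording in three places and occasional extra contacts. Some late events will be confounded by later therapy. Section 6.7 already records subsequent anticancer treatment, so its start date can be shown beside them.

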## 6.6 **Duration of Follow-Up**

Patients who complete the maximum number of cycles or who met off-therapy criteria other than disease progression will be asked to participate in study follow-up and be evaluated at month 2 ( $\pm$  1 week), month 4 ( $\pm$  2 weeks), month 6 ( $\pm$  4 weeks), month 9 ( $\pm$  4 weeks), and month 12 ( $\pm$  2 months) and then yearly until year 5, or until disease progression.

Follow-up visits will be completed in-person unless the patient does not agree to continue in-person visits. In this case, telephone contact may be arranged to ensure the collection of as many safety and efficacy parameters as possible. The approach taken should be recorded in the CRF. A patient that agrees to modified follow-up is not considered to have withdrawn consent or to have withdrawn from the study.

Patients who develop disease progression during combination therapy will be followed for a minimum of 30 days after the last dose of study drug or study procedure, or until death, whichever occurs first. Patients removed from study for unacceptable adverse event(s) will be followed until resolution or stabilization of the adverse event and disease progression, whichever occurs later.

#### 6.7 General Concomitant Medication

Medications, including reason for use, date(s) of administration, and dosage information, taken within 28 days prior to the start of treatment will be recorded. Concomitant medications, including medications for AEs, will continue to be recorded up to 30 days after treatment discontinuation. This includes any medication or vaccine, including over-the-counter or prescription medicines, vitamins, and/or herbal supplements. The investigator should be alerted if the patient is taking any agent known to affect the study agent(s) or with the potential for drug interactions. Following treatment discontinuation, information on subsequent anti-cancer therapies will be recorded.

Because there is a potential for interaction of Hu5F9-G4 (magrolimab) and Dinutuximab with other concomitantly administered drugs, the case report form must capture the concurrent use of all other drugs, over-the-counter medications, or alternative therapies. The Principal Investigator should be alerted if the patient is taking any agent known to affect or with the potential for drug interactions. The study team should check a frequently updated medical reference for a list of drugs to avoid or minimize use of.

For all prohibited and/or restricted concomitant medications, treatment and supportive care while receiving protocol therapy, please refer to inclusion/exclusion criteria (section 3.0).

Pharmacologic doses of systemic corticosteroids should be used ONLY for life-threatening conditions (i.e. life-threatening allergic reactions and anaphylaxis such as bronchospasm, stridor) unresponsive to other measures. The use of dexamethasone as an anti-emetic is not permitted. Corticosteroid therapy can be used as a premedication for transfusion in patients known to have a history of transfusion reactions or for treatment of an unexpected transfusion reaction (hydrocortisone 2 mg/kg or less or an equivalent dose of an alternative corticosteroid). The use of steroids during protocol therapy requires clear justification and documentation.

Patients who use oral contraceptives should continue their use. Males and females of reproductive potential should use highly effective means of contraception (refer to section 6.8).

### **6.7.1** Hu5F9-G4 (magrolimab) Excluded Therapies

Any concomitant therapy intended for the treatment of cancer, whether health authority approved or experimental, is prohibited unless it is specifically included in the treatment regimen described in this protocol. There are no studies regarding drug-drug interactions conducted with Hu5F9-G4 (magrolimab).

### **6.7.2** Dinutuximab Excluded Therapies

Any concomitant therapy intended for the treatment of cancer, whether health authority approved or experimental, is prohibited unless it is specifically included in the treatment regimen described in this protocol. There are no studies regarding drug-drug interactions conducted with dinutuximab.

#### 6.8 Contraception

The effects of Hu5F9-G4 (magrolimab) monoclonal antibody on the developing human fetus are unknown and dinutuximab is known to be teratogenic.

A woman is of childbearing potential if she is postmenarcheal, has not reached a postmenopausal state ( $\geq$  12 continuous months of amenorrhea with no identified cause other than menopause), and has not undergone surgical sterilization (removal of ovaries and/or uterus).

Females of childbearing potential must have a negative urine or serum pregnancy test within 30 days of enrollment and within 72 hours prior to treatment initiation. Additional pregnancy tests (serum or urine) should be obtained throughout the study in accordance with local policy.

Female patients of childbearing potential must be willing to use one highly effective method of contraception (hormonal or barrier method of birth control; abstinence) prior to study entry, during the study and continue for 4 months after the last dose of study treatment. Should a woman become pregnant or suspect she is pregnant while she or her partner is participating in this study, she should inform her treating physician immediately.

- Examples of contraceptive methods with a failure rate of < 1% per year include: bilateral tubal ligation, male sterilization, and established proper use of hormonal contraceptives that inhibit ovulation, hormone-releasing intrauterine devices, and copper intrauterine devices.
- Hormonal contraceptive methods must be supplemented by a barrier method plus spermicide.
- The reliability of sexual abstinence should be evaluated in relation to the duration of the clinical trial and the preferred and usual lifestyle of the patient. Periodic abstinence (e.g., calendar, ovulation, symptothermal, or postovulation methods) and withdrawal are not acceptable methods of contraception.

Male patients who are sexually active with a woman of childbearing potential (WOCBP) and who have not had vasectomies must be willing to use a barrier method of contraception (condom plus spermicidal gel) and refrain from sperm donation during the study and for 4 months after the last dose of study treatment. If the partner is pregnant, male patients must use barrier method contraception (condom) during the study and for 4 months after the last dose of study treatment to prevent fetal exposure to study treatment.

